1.2 BACKGROUND AND RATIONALE

1.2.1 HPV Associated Malignancies

In the United States, there are more than 30,000 cases of HPV associated cancer annually (1) (Table 1). Metastatic HPV associated malignancies (cervical, anal, oropharyngeal cancers etc.) are often incurable and poorly palliated by standard therapies. Responses to chemotherapy are variable but generally short-lived with median PFS around 3 to 7 months (2-5). In a Gynecologic Oncology Group randomized trial comparing four cisplatin-based doublets as first line therapy for metastatic cervical cancer the response rates were 22-29% and median PFS was 4 to 6 months with median OS 10 to 13 months (6). The addition of bevacizumab to combination chemotherapy has been reported to increase OS by 3.7 months, but virtually all patients die of their disease within 2 years (7). Randomized trials of second line therapy are lacking but response rates for single agents are generally reported to be less than 20% (8). Early evidence suggests that immune checkpoint therapy also has a low response rate in this disease with a phase 1b trial (KEYNOTE 028) showing a 12.5% response rate (3/24 patients) and a phase II study showing a response rate of 13.3% (13/98 patients) to pembrolizumab in patients with recurrent or metastatic cervical cancer (9).

Table 1: Estimated annual incidence of HPV associated cancers in the US

Site	Incidence of HPV associated cancers	Cases attributed to HPV (%)
Oropharyngeal	15,738	11,000 (70.1%)
Cervix	11,771	10,700 (90.6%)
Vulvar	3554	2400 (68.8%)

Site	Incidence of HPV associated cancers	Cases attributed to HPV (%)
Vaginal	802	600 (75%)
Penis	1168	700 (63.3%)
Rectal (squamous cell)	750	700 (91.1%)
Anus	5,010	4,600 (91.1%)
Total	38,793	30,700 (79.1%)

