Where clinically appropriate subjects enrolled on Arm 1 will receive one year of treatment during which subjects will be followed with surveillance scans using CT/MRI (as appropriate) every 6-12 weeks. On a case by case basis treatment beyond a year is allowed per investigator discretion. Subjects with evidence of disease progression after completing a year of treatment will be allowed retreatment. Patients might be taken off treatment for disease progression prior to completing one year of treatment, but where clinically appropriate, treatment beyond radiographic progression is allowed if in the opinion of the investigator the subject is benefiting from treatment. Subjects will be taken off treatment if unacceptable toxicity occurs and is attributed to all therapeutic agents. If a single agent is tolerated that agent may be continued.

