6. Participants who have come off treatment for disease progression will be followed by phone annually for survival. Participants who have not progressed on treatment will continue to be followed and scanned per investigator discretion until progression. Initial and follow up courses of treatment may extend beyond a year per investigator discretion.

7. As indicated in Section **12.3**, all subjects will be offered the opportunity to complete an NIH advanced directive form. This should be done preferably at baseline but can be done at any time during the study as long as the capacity to do so is retained. The completion of the form is strongly recommended, but is not required.

8. Biochemical profile: Acute care, hepatic and mineral panel as described in Sections **2.2** and **2.4**.

9. Evaluate CEA, CA19-9, CA125 and CA15-3 at baseline and follow elevated values thereafter (for participants enrolled on the phase I portion of the protocol).

10. In HIV positive participants.

11. Every 8 weeks for participants.

12. Imaging will be performed every 8 weeks. In the event of a PR or CR tumor imaging assessments may be performed every 3 months (+/- 2 weeks) at the discretion of the investigator. Tumor assessment should be continued beyond end of treatment in participants who have not experienced PD until they experience PD in order to assess PFS. MRI (with gadolinium) will be used when CT scan is not an option to follow the disease. Bone scans and other imaging assessments may also be performed as clinically indicated.

13. In participants with known CNS disease as described in Section 2.1.2.3; MRIs may be performed as clinically indicated in this population.

14. Where feasible, optional biopsies may be done at baseline and at week 9 and will likely be CT guided. If a recent (\leq 6 months preferred) outside biopsy has been performed that specimen may be used in lieu of a baseline biopsy for both phase I and II participants.

15. Where feasible, research blood (see Section 5.1) will be collected at the following time points:

- PKs and ADAs – performed only on Arm 1B (bintralusp alfa plus vaccine)
 - Samples for PK analysis will be taken prior to infusion and following infusion on W1 and W5 and prior to infusion on W3 and W11 or with end of treatment labs if patients comes off treatment prior to any of those timepoints; and

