6. Participants who have completed neoadjuvant or induction immunotherapy on the phase II portion of the protocol will be followed by phone or email for recurrence, adverse events and survival starting 2 months (+/- 2 weeks) after safety visit and then annually (+/- 1 month) until the patient is 5 years out from surgery or completion of chemoradiotherapy.

7. As indicated in Section **12.3**, all subjects will be offered the opportunity to complete an NIH advanced directive form. This should be done preferably at baseline but can be done at any time during the study as long as the capacity to do so is retained. The completion of the form is strongly recommended but is not required.

8. Biochemical profile: Acute care, hepatic and mineral panel as described in Sections **2.2** and **2.4**.

9. In HIV positive participants.

10. Imaging (CT of neck and chest/ MRI, if indicated, for oropharyngeal cancer participants; CT of skull, neck and chest/ MRI, if indicated, for sinonasal SCC; no CT chest required if PET/CT available) at baseline/screening, and at Week 4-5 (CT of neck/ MRI, if indicated, for oropharyngeal cancer participants; CT of skull, neck/ MRI, if indicated, for sinonasal SCC). MRI (with gadolinium) will be used when CT scan is not an option to follow the disease. Bone scans and other imaging assessments may also be performed as clinically indicated. Post-treatment imaging is to be strongly pursued but is not required and may be waived at the discretion of the PI.

11. Where feasible, biopsies will be done at baseline as well as at week 4-5. Biopsies will be done by ENT under direct visualization. Where feasible at least 2 cores will be obtained. If a recent (\leq 6 months preferred) outside biopsy has been performed that specimen may be used in lieu of a baseline biopsy. For patients that have surgery as definitive treatment, Week 4-5 biopsy may be omitted: in this case tumor biospecimens will be obtained from the institution where the patient underwent surgery after the patient signs that institution's release document.

12. Where feasible, research blood (see Section **5.1**) will be collected at baseline, week 3 and week 45 with the following exceptions:

- Samples for AVA analysis will be taken prior to infusion on W1, W3, with research labs on 4-5 or with end of treatment labs if participants come off treatment prior to any of those timepoints.
- Note: Samples may be sent to Precigen, Inc for additional analyses (see Section **5.1.9**).

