Tumor responses to treatment will be assigned based on the evaluation of the response of target, non-target, and new lesions according to RECIST 1.1 (all measurements should be recorded in metric notation).

To assess objective response, the tumor burden at baseline will be estimated and used for comparison with subsequent measurements. At baseline, tumor lesions will be categorized in target and non-target lesions according to RECIST 1.1.

Results for these evaluations will be recorded with as much specificity as possible so that pre-and post-treatment results will provide the best opportunity for evaluating tumor response.

Any CR or PR should be confirmed according to RECIST 1.1. In the case of a PR or CR, a confirmatory CT or MRI scan should be done no sooner than 4 weeks (preferably at the scheduled 6-week interval).

The Investigator may perform scans in addition to a scheduled trial scan for medical reasons or if the Investigator suspects PD.

As an exploratory endpoint antitumor activity will also be evaluated according to iRECIST (52).

Using iRECIST criteria the following will be incorporated into assessment:

1. An increase in the sum of target lesions of more than 20%, unequivocal increase in non-target lesions or new lesions result in iUPD (unconfirmed progressive disease); iUPD can be assigned multiple times as long as iCPD (confirmed progressive disease) is not confirmed at the next assessment.
2. Progression is confirmed in the target lesion category if the next imaging assessment after iUPD (4–8 weeks later) confirms a further increase in sum of measures of target disease from iUPD, with an increase of at least 5 mm. Progression is confirmed in the non-target lesion category if subsequent imaging, done 4–8 weeks after iUPD, shows a further unequivocal increase in non-target lesions. Progression is confirmed in the new lesions category if at next assessment additional new lesions appear or an increase in size of previously seen new lesions is seen (≥ 5 mm for sum of new lesion target).

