6.3.5.3 Evaluation of Best Overall Response

The best overall response is the best response recorded from the start of the treatment until disease progression/recurrence (taking as reference for progressive disease the smallest measurements recorded since the treatment started). The participant's best response assignment will depend on the achievement of both measurement and confirmation criteria.

For Participants with Measurable Disease (i.e., Target Disease)

Target Lesions	Non-Target Lesions	New Lesions	Overall Response	Best Overall Response when Confirmation is Required*
CR	CR	No	CR	≥ 4 wks. Confirmation**
CR	Non-CR/Non-PD	No	PR	≥ 4 wks. Confirmation**
CR	Not evaluated	No	PR	
PR	Non-CR/Non-PD/not evaluated	No	PR	
SD	Non-CR/Non-PD/not evaluated	No	SD	Documented at least once ≥ 6 wks. from baseline**
PD	Any	Yes or No	PD	no prior SD, PR or CR
Any	PD***	Yes or No	PD	
Any	Any	Yes	PD	

Target Lesions	Non-Target Lesions	New Lesions	Overall Response	Best Overall Response when Confirmation is Required*
*	See RECIST 1.1 manuscript for further details on what is evidence of a new lesion.			
**	Only for non-randomized trials with response as primary endpoint.			
***	In exceptional circumstances, unequivocal progression in non-target lesions may be accepted as disease progression.			
Note:	Participants with a global deterioration of health status requiring discontinuation of treatment without objective evidence of disease progression at that time should be reported as “ symptomatic deterioration .” Every effort should be made to document the objective progression even after discontinuation of treatment.			

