10.3 POPULATIONS FOR ANALYSES

All participants who receive any investigational treatment will be evaluable for safety and toxicity evaluations.

For phase II, only HPV-OPC participants will be evaluable for primary and secondary objective endpoints. HPV-SNSCC participants will be evaluable only for exploratory objectives.

For phase II, participants who receive at least two doses of therapy and have an adequate pretreatment and posttreatment biopsy will be evaluable for immune infiltration assessments. For phase II, participants who receive at least two doses of immunotherapy and go on to receive standard definitive therapy will be evaluable for relapse free survival and overall survival assessments.

For phase I and II participants, only those participants who have measurable disease present at baseline and have had their disease re-evaluated will be considered evaluable for response. (Note: Participants who exhibit objective disease progression prior to the end of cycle 1 will also be considered evaluable.)

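### Phase I ORR omits treated participants who die, deteriorate or withdraw before any re-evaluation and without objective progression, so it can only be biased upward

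*Combined protocol and SAP*

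**What the plan says.** Section 10.3 sets one response-evaluability rule for both phases: "only those participants who have measurable disease present at baseline and have had their disease re-evaluated will be considered evaluable for response". Its note makes one exception: "Participants who exhibit objective disease progression prior to the end of cycle 1 will also be considered evaluable". Dosing and visits are scheduled by day and week, and no cycle is defined anywhere.

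For Phase I, note 12 of the study calendar (3.4.1) says "Imaging will be performed every 8 weeks". The text after the DLT definition in section 3.1 gives a different interval: "surveillance scans using CT/MRI (as appropriate) every 6-12 weeks". The calendar marks no tumor evaluation at the end-of-treatment or safety follow-up visit. Section 6.3.4 permits unscheduled imaging but does not require it: "The Investigator may perform scans in addition to a scheduled trial scan for medical reasons or if the Investigator suspects PD".

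Section 6.3.5.3 foresees this group: "Participants with a global deterioration of health status requiring discontinuation of treatment without objective evidence of disease progression". It asks that they be reported as symptomatic deterioration and that progression be documented later if possible. It does not place them in the ORR denominator. Sections 10.4.3 and 10.4.4.2 do not say how a participant with no post-baseline assessment is scored.

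ORR is a secondary objective in Phase I (1.1.2). Objective response in Phase II is exploratory (1.1.3), and note 10 of the Phase II calendar (3.4.2) says: "Post-treatment imaging is to be strongly pursued but is not required and may be waived at the discretion of the PI".

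**The concern.** A response rate estimates the chance of response among those who start treatment. Removing people because an outcome could not be observed is harmless only if the reason is unrelated to response. Here the main reasons, death and clinical decline before the first assessment, are themselves treatment failures. The numerator is untouched while the denominator shrinks.

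The expansion of Arm 1B exists to gauge preliminary efficacy in 10 evaluable participants. With a denominator that small, one or two omissions move the rate by several percentage points. A reader will naturally set the result beside the response rates in section 1.2.5 (12-24% for PD-1/PD-L1 blockade alone, 35% for M7824 in HPV-associated cancers) without seeing that the denominator was selected.

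**Working it through.** **The plan's own figure.** The plan gives no target, power or precision for ORR. Its only design calculation (10.2) is for the Phase II CD3+ endpoint: n = 20, 50% versus 80%, one-sided 0.05, exact binomial, stated power 80.4%. With success declared at 15/20 or more, power is 0.8042 and exact alpha 0.0207, so it reproduces. The present point does not affect it.

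**Direction.** Let k be the responders, E the evaluable participants and m the treated participants with measurable disease but no re-evaluation and no objective progression. The plan reports k/E; the all-treated rate is k/(E+m). With u = m/(E+m), the reported rate equals the all-treated rate divided by (1-u). The factor is never below 1, so the bias is upward (or nil when k = 0).

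**Rough size of u.** The documents do not give it. As a proxy, take death before the first scan at week 8 of the calendar, with exponential survival:

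P(death by day 56) = 1 - 2^(-t/M), where t = 56/30.44 = 1.84 months and M is median OS in months (section 1.2.5).

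| Source of M | M | P(death by week 8) |
|---|---|---|
| PD-1/PD-L1 alone, low end | 7.5 | 15.6% |
| PD-1/PD-L1 alone, high end | 11.5 | 10.5% |
| Earlier M7824 HPV cohort | 16.2 | 7.6% |

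Reaching 10 evaluable would then take 10/(1-0.076) = 10.8 to 10/(1-0.156) = 11.8 treated, so about 1 to 2 are lost. The inflation factor runs from 1/(1-0.076) = 1.08 to 1/(1-0.156) = 1.18.

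The proxy errs both ways. It is too high where progression was documented before death. It is too low because it leaves out clinical deterioration and withdrawal.

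**Effect on Arm 1B (10 evaluable, illustrative responder counts).**

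| Responders | Reported | 1 omitted | 2 omitted |
|---|---|---|---|
| 3 | 3/10 = 30.0% | 3/11 = 27.3% | 3/12 = 25.0% |
| 4 | 4/10 = 40.0% | 4/11 = 36.4% | 4/12 = 33.3% |

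The shift is about 3 to 7 percentage points. Exact 95% intervals are 6.7-65.2% for 3/10, 6.0-61.0% for 3/11 and 5.5-57.2% for 3/12.

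**Phase II, for illustration.** If all 20 participants had measurable disease and 4 responded, the rate is 4/20 = 20.0%. Two waived scans among the others make it 4/18 = 22.2%, and four make it 4/16 = 25.0%. This shows sensitivity to a discretionary scan, not a known bias.

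**The case against.** The strongest reply is that the gap is narrow, and much of it is right. Several stronger readings are tempting, but the documents do not support them.

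- **That all early failures are left out.** Anyone with documented progression by week 8 has been re-evaluated, or falls under the note, and counts as a non-responder. Section 6.3.5.3 also asks for progression to be sought after treatment stops.
- **That the loss can be read from PFS.** Section 1.2.1 describes chemotherapy responses as "generally short-lived with median PFS around 3 to 7 months". The same formula then gives 34.6% (median 3 months) to 16.7% (7 months) with an event by day 56. This is at most a ceiling: it counts every event, including documented progressions that stay in, and the medians come from chemotherapy-treated metastatic disease.
- **That stopping for toxicity removes a participant.** Note 12 of the Phase I calendar continues tumor assessment after treatment ends until progression. Only someone who also dies, withdraws or cannot return is lost.
- **That only re-imaged participants count.** The rule requires re-evaluation. Sections 6.3.1 and 6.3.4 allow physical examination as a tumor measure.
- **That unscanned failures in Arm 1B are replaced.** The only explicit replacement rule (section 3.1) concerns HPV status. Section 10.2 allows for a few inevaluable participants without defining them. Table 8 shows 11 treated against a target of 10 evaluable, but gives no reason and shows no exclusion.
- **That Phase II has the same bias.** Those participants are newly diagnosed and receive two vaccine doses before definitive therapy. A waived scan is missing data, not a shown failure, and counting it as non-response could bias that exploratory rate downward.
- **That a decision rests on the ORR.** The plan has no ORR test, threshold or go/no-go rule, and Arm 2B is closed.

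What survives is that no provision counts death, symptomatic deterioration or withdrawal before any re-evaluation as non-response, and the one exception depends on an undefined cycle.

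**Conclusion.** The concern holds for the Phase I ORR in this limited form: the stated rule drops a group made up entirely of non-responders, so the bias has a known sign. The size is uncertain and probably modest: about 1-2 participants per 10 evaluable, or 3 to 7 percentage points at a reported ORR of 30-40%. That rests on exponential survival, on background OS medians from other cohorts, and on early death standing in for loss without objective progression. Sampling error at n = 10 is far larger, but a wide interval does not remove a one-sided bias that wording can prevent. In Phase II the issue is transparency about discretionary missing scans on an exploratory endpoint. The 8-week and 6-12-week imaging statements must also be reconciled, because they determine when a first scheduled re-evaluation is due.

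**What to change.** In section 10.3:

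1. Make the main Phase I ORR denominator all treated participants with measurable disease at baseline, separately for Arm 1A and Arm 1B. Count those with no post-baseline assessment as non-responders, whatever the reason. Measurable disease is already a Phase I entry criterion (2.1.1.3), so this is in effect everyone treated.
2. Keep the re-evaluated set as a supporting display. Retain the early-progression note, because deleting it would remove that display's explicit protection for early progressors, but replace cycle 1 with a defined time point.
3. For the exploratory Phase II response rate, report the number of waived or missing scans with reasons. Show the rate in all treated participants with measurable disease and in the re-evaluated set.
4. Reconcile the Phase I imaging interval in section 3.1 with note 12 of the calendar.

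The cost is a few sentences, one extra row in the Phase I response table, and a short listing of missing Phase II scans. No new participants or visits are needed, and the change remains possible after enrollment. The downside is that the stated ORR may be slightly less favourable.

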10.4 STATISTICAL ANALYSES

10.4.1 General Approach

The phase I portion of the study will be conducted as a safety assessment using a 3+3 dose escalation design. In addition, Arm 1B will be expanded to a total of 10 evaluable participants to gauge the preliminary efficacy of the combination of PRGN-2009 and M7824 in participants with advanced disease. The phase II portion of the study will be conducted to evaluate for a potentially significant increase in CD3+ tumor infiltrating lymphocytes with immunotherapy induction.

10.4.2 Analysis of the Primary Endpoints

Regarding the phase I portion of the study, participants will be evaluated with respect to the grades and types of toxicities obtained. The results will be presented descriptively and tabled if appropriate. Regarding the phase II portion of the study the rate of doubling of baseline CD3+ tumor infiltrating lymphocytes will be provided as well as the 95% confidence interval.

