6.3.6.3 Digital Imaging Protocol: Once all antigens of interest are stained, a multiplex scanning protocol will be created on Vectra Polaris scanner (Akoya/PerkinElmer), to allow for whole slide imaging at 10-20X. This is followed by higher resolution scan of regions of interest (ROIs) picked (5 on average) or whole slide analysis (if feasible) by research pathologist (GMB TIME Laboratory). The scans generated at high resolution are called multispectral images (MSIs) and are available in .im3 format. These can only be analyzed using inform software (available in GMB TIME Laboratory). The software allows for spectral unmixing based on a spectral library (built based on single reference stains) and artificial intelligence based unmixing algorithm. Individual ROIs will be segmented based on nuclear counterstain DAPI, and cells will be counted based on expression of various markers (CD3, CD4, CD8) in a binary fashion allowing for objective measurements of density, absolute counts, and percentages of each cell type. Averages of representative ROIs or whole areas of interest (if feasible) for each time point will be generated for statistical analysis.

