10 STATISTICAL CONSIDERATIONS

10.1 STATISTICAL HYPOTHESIS

10.1.1 Primary Endpoints

10.1.1.1 Phase I:

The primary endpoint of the phase I portion of the study is to determine the recommended phase II dose (RP2D) of PRGN-2009 (HPV vaccine) alone and in combination with M7824.

10.1.1.2 Phase II:

The primary endpoint of the phase II portion of the study is to determine if HPV vaccine alone (Arm 2A) is able to result in a ≥ 2 -fold increase in CD3+ tumor infiltrating T cells post treatment compared with pre-treatment in participants with p16+ oropharyngeal cancer.

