10.2 SAMPLE SIZE DETERMINATION

The phase I portion of the trial will be conducted using 3+3 dose escalation design evaluating the safety of PRGN-2009 at two dose levels as monotherapy and at the RP2D of PRGN-2009 in combination with a fixed dose of M7824. Using this design up to 22 participants may be enrolled on the phase I portion of the study.

In arm 2A, phase II, 20 participants with p16+ oropharyngeal cancer will be enrolled based on the following reasoning. Assume that a success for any individual participant will be defined as that participant experiencing a two-fold increase in CD3+ tumor infiltrating T cells post treatment compared with pre-treatment. With 20 participants, there would be 80.4% power to detect a difference between 50% and 80% of participants experiencing a success in arm 2A, with an exact binomial test using a one-sided 0.05 significance level. As an illustration, with 20 participants, if 15 participants were able to have a two-fold increase, the lower two-sided 90% confidence bound on 15/20 is 54.4% and the upper two-sided 90% confidence bound is 89.6%. Thus, 15/20 participants would demonstrate the intended magnitude of effect. If 14/20 had this outcome, the lower 90% two-sided bound is 49.2% and the upper two-sided 90% bound is 86.0%, essentially demonstrating nearly the same result.

Expecting that up to 22 evaluable participants will enroll on the phase I portion of the study, that 20 evaluable p16+ oropharyngeal cancer participants will enroll on phase II 2A, and that up to 2 evaluable HPV-SNSCC participants may enroll on phase II 2A, a total of up to 44 evaluable participants will be planned to enroll on this protocol. To allow for a few inevaluable participants the accrual ceiling for this protocol will be set at 50 participants.

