10.4.9 Exploratory Analyses (Immune Responses)

Where feasible, exploratory immune analyses will be conducted to evaluate anti-tumor immune responses. Immune response will be assessed among all subjects treated in each cohort. The

magnitude of immune responses will be described. A subject will be considered evaluable for immune response if they receive at least one dose of treatment. The percentage of subjects with a positive immune response will be evaluated by cohort. For flow cytometry analyses on PBMC samples, Student T tests or Kruskal-Wallis and Wilcoxon rank sum tests as appropriate will be performed on percentages of TNF- α and/or IFN- γ expressing cells among the different cohorts to determine any significant differences in cell populations. For antigen specific T cell responses, a positive immune response is defined by CMI reactivity in *ex vivo* stimulation using a flow cytometric readout (cytokine production or CD107 expression). Antigen-specific peptide challenge assays require a readout of >250 reactive T-cells/million cells above the background (53).

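### Does the phase II primary analysis need a planned estimate of how large the paired CD3+ change is, beyond the doubling rate?

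*Combined protocol and SAP*

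**What the plan says.** Section 10.1.1 sets the phase II primary endpoint as an at least two-"fold increase in CD3+ tumor infiltrating T cells post treatment compared with pre-treatment in participants with p16+ oropharyngeal cancer". Section 10.2 turns this into a yes/no outcome for each person: "a success for any individual participant will be defined as that participant experiencing a two-fold increase in CD3+ tumor infiltrating T cells". It then sizes Arm 2A at 20 participants with a one-sided exact binomial test of 50% against 80%. Section 10.4.2 reports that same quantity: "the rate of doubling of baseline CD3+ tumor infiltrating lymphocytes will be provided as well as the 95% confidence interval".

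The underlying data are richer than a yes/no. Section 10.3 states that "participants who receive at least two doses of therapy and have an adequate pretreatment and posttreatment biopsy will be evaluable for immune infiltration assessments". Section 6.3.6 describes an imaging assay that gives "objective measurements of density, absolute counts, and percentages of each cell type", and adds: "Averages of representative ROIs or whole areas of interest (if feasible) for each time point will be generated for statistical analysis".

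Two other places touch on size. Section 10.4.9, which is exploratory, says the "magnitude of immune responses will be described", with its own evaluability rule: "A subject will be considered evaluable for immune response if they receive at least one dose of treatment". Section 10.4.8 permits, but does not require, a waterfall or spider plot of individual responses.

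**The concern.** A measured ratio is reduced to whether it reaches two, and the plan names no summary of the ratio itself for the oropharyngeal cohort. A cohort whose participants mostly just pass two-fold and one whose participants mostly reach five-fold could give the same rate and the same interval. Someone deciding on a follow-on trial would want to know which had occurred, and section 1.2.11 rests the choice of endpoint on the link between greater T-cell infiltration and survival.

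The nearby text does not clearly fill the gap. Section 10.4.9 names no tissue CD3+ estimator or interval, its detailed methods concern blood-cell flow cytometry and antigen-specific responses, and its one-dose rule differs from the two-dose, paired-biopsy rule in 10.3. The plot in 10.4.8 is optional. The only objective that speaks of differences in CD3+ cells (section 1.1.3) covers the sinonasal group of up to 2 participants.

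**Working it through.** **1. The plan's own figures.** Inputs from section 10.2: n = 20, null 50%, alternative 80%, one-sided exact binomial test at 0.05.

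- P(X ≥ 14 | 0.5) = 0.0577, above 0.05; P(X ≥ 15 | 0.5) = 0.0207. The cut-off is therefore 15.
- Power = P(X ≥ 15 | 0.8) = 0.8042, matching the stated 80.4%.
- Clopper-Pearson 90% limits: 15/20 gives 54.4% to 89.6%; 14/20 gives 49.2% to 86.0%. Both match.
- The 95% interval that 10.4.2 would report for 15/20 is 50.9% to 91.3%, which excludes 50%. At n = 20 the reported interval agrees with the test at its cut-off.

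**2. What the doubling rate leaves open.** The documents give no SD for the paired change, so one is assumed. If log2(post/pre) is normal with standard deviation SD and a proportion p double, the median fold change is 2^(1 + z_p × SD). With p = 0.80, z_p = 0.8416:

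| Assumed log2 SD | Median fold change |
|---|---|
| 0.5 | 2^1.421 = 2.68 |
| 1.0 | 2^1.842 = 3.58 |
| 1.5 | 2^2.262 = 4.80 |

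In each row 16 of 20 doubling would be reported as 80% (exact 95% CI 56.3% to 94.3%). The loss of information is real.

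**3. What an added interval would give back.** A natural addition is the median fold change with the order-statistic interval from the 6th to the 15th of 20 ordered values, with coverage 1 − 2 × 0.0207 = 95.9%. In simulation at an 80% doubling rate it typically runs from 2.2 to 3.3, 2.4 to 5.4 and 2.6 to 8.8 for the three SDs. The three ranges overlap and their lower limits are close together, so at n = 20 the interval separates just over two-fold from much larger only weakly.

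**4. Whether it would sit cleanly beside 10.4.2.** The attraction of this interval is that, with ranks tied to the binomial cut-off c (from n − c + 1 to c), its lower limit is at least two-fold exactly when the cut-off is met. Section 10.4.2, however, reports a 95% interval for the rate, so that comparison matters when fewer than 20 pairs are evaluable:

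| n | Cut-off c | Median-interval coverage | Exact 95% CI for c/n |
|---|---|---|---|
| 20 | 15 | 95.9% | 50.9% to 91.3% |
| 19 | 14 | 93.6% | 48.8% to 90.9% |
| 18 | 13 | 90.4% | 46.5% to 90.3% |
| 17 | 13 | 95.1% | 50.1% to 93.2% |

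At n = 18 and 19 the median interval would lie wholly at or above two-fold while the reported 95% interval for the rate still included 50%. An interval with at least 95% coverage at every n removes the mismatch in confidence level, but gives up the exact tie to the cut-off at n = 18 and 19.

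**The case for a change.** The strongest case for a change is that it is nearly free. The paired values will exist, a median and a display of individual values need only a few lines of text, and naming the summary in advance prevents a later choice among flattering ones. The general sentence in 10.4.9 is not a specification, and as the text stands no estimator or interval is named. All of that is fair, and it makes the addition a reasonable courtesy to readers.

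It does not make the plan deficient. Section 6.3.6, headed as immune response evaluation, opens with biopsies stained for CD3 among other markers, so the promise in 10.4.9 to describe the size of immune responses can reasonably be read to include them. The one-dose rule there is no real obstacle: 10.3 sets a specific rule for immune infiltration, and a fold change cannot be computed without both biopsies.

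A sharper argument is that 6.3.6 lists density, counts and percentages without choosing one, and that no rule covers a zero baseline. Both could change who counts as having doubled. That concerns how the primary endpoint itself is defined and deserves to be considered separately. Adding a fold-change estimate would not settle it; the estimate would inherit the same ambiguity.

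**Conclusion.** No change to the plan is called for. The observation is accurate: no fold-change estimator or interval is named for the oropharyngeal cohort, and an 80% doubling rate is compatible with median changes from 2.7-fold to 4.8-fold over assumed log2 SDs of 0.5 to 1.5. But the plan answers the question it asks. Objective, endpoint, sample size and analysis share one responder definition, the power of 80.4% reproduces, and the test and its conclusion would be the same with or without the supplement. A rate with its interval is a sound primary report for a single-arm study of 20 participants. The description of size is a gap that analysts can fill sensibly under 10.4.9 and 10.4.8, by listing the paired values and quoting a median. The gain from fixing a particular interval in advance is modest at this sample size, and the most obvious choice brings a mismatch of its own at 18 or 19 evaluable pairs. The fold-change figures rest on assumed SDs and a log-normal shape; the binomial results do not.
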